13.5 Interim Monitoring

The study team will continuously monitor study accruals, toxicities and clinical outcome. Early stopping for futility will be considered after 15 patients have been enrolled and treated in each arm. Using a Minimax design, the chance of early stoppage under the null is calculated at 65%. The median time to response for nivolumab is 2 months. Once subject 15 is enrolled for each arm, we will wait a minimum of 8 (median time to response) and maximum of 12 weeks (2 MRI cycles) to assess response if an objective response by iRANO has not been noted in the already accrued patients.

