Cohort 2 of CheckMate 143 (CA209143) was a randomized phase 3, open-label study comparing nivolumab monotherapy with bevacizumab for recurrent glioblastoma. Toxicity profile was comparable to other cancers. Nivolumab did not meet the primary endpoint of superior OS when compared with bevacizumab (HR = 1.04; P = 0.76, see Figure below).

Objective response rate (ORR) with nivolumab was lower than bevacizumab (7.8% vs. 23.1%), while stable disease was noted in 21.6% and 46.8%, respectively. There was a longer time to best response (3.0 vs. 1.5 months) as well as prolonged response duration (11.1 vs. 5.3 months) with nivolumab compared to bevacizumab. As a single agent, nivolumab revealed minimal and delayed but durable response in recurrent glioblastoma

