13. STATISTICAL CONSIDERATIONS

13.1 Study Design and Sample Size

We propose an open label, two parallel arm, two-stage, phase II trial to determine the efficacy, in terms of objective response rate (ORR), of combination therapy with tumor treating fields (TTFields) therapy, nivolumab with or without ipilimumab in adult patients with bevacizumabnaïve, recurrent glioblastoma. Best objective response rate (ORR) is defined as the proportion of evaluable patients who achieve complete (CR) or partial response (PR) according to modified immunotherapy iRANO criteria. Secondary objectives include safety, ORR by standard RANO criteria, overall survival (OS), progression-free survival (PFS), clinical benefit (defined as ORR plus stable disease >12 weeks), compliance rates of TTFields therapy at or above goal of 75%, and exploratory correlations between response or survival and compliance rates, serum and/or tumor tissue biomarkers. Primary analyses are performed for each arm, but secondarily assessed for the entire cohort as well.

The EF-11 study showed a response rate of 14% among patients with recurrent glioblastomas treated with TTFields alone compared to physician's choice medical therapy (Stupp et al, Eur J Cancer 2012). Thus, the null H0 is set at 14% and H1 (target ORR) set at 35% for each arm. Power is set at 85% with a 1-sided alpha of 0.05.

If no response is seen after 15 eligible patients are accrued in either arm, that arm will close for futility. Based on a MiniMax design, if >2 responses are seen on the first 15 patients in either arm, then 15 more patients will be accrued in the arm. If \geq 7 responses are seen among the 30 patients in either arm, this regimen deserves further investigation. Sample size will be 30 maximum per cohort/arm for a total of 30 to 60 subjects enrolled on study.

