13.2 Definitions

Evaluable: All study-eligible patients who receive at least one infusion of nivolumab will be considered *evaluable for safety and toxicity*. To be *evaluable for efficacy*, patients must be study eligible, receive at least one cycle (6 weeks) of immunotherapy and complete initial disease assessment at ≥ 6 weeks after starting therapy.

Exclusions: Any patient who is enrolled on study, but does not receive any component of study treatment, will be excluded from all efficacy analyses. Any patient who initiates treatment and is later found to be ineligible for study (e.g., protocol violation) will be withdrawn from study but will be followed for disease progression, toxicity and survival. The experience of such patients will be characterized separately from that of evaluable patients. Reasons for exclusion of enrolled patients from the analysis set for efficacy, or for safety, will be characterized.

Overall response rate (ORR): Overall response rate is the proportion of patients whose best overall response per modified iRANO criteria or standard RANO criteria is complete (CR) or partial (PR) after at least 6 weeks from start of therapy. iRANO additionally requires best overall response of CR or PR to be sustained, that is, confirmed by a second assessment at \geq 4 weeks later. Patients who clinically progress before the initial radiographic assessment after 1 cycle (6 weeks) will be considered nonresponders.

Progression-free survival (PFS): PFS will be measured from the start date of treatment until

documented evidence of disease progression, clinical progression or death from any cause, after at least 8 weeks from start of therapy. Radiographic progression should be confirmed by a second assessment at \geq 4 weeks later. For patients who remain alive without progression, follow up time will be censored at the date of last assessment.

Overall survival (OS): Survival will be measured from the start date of treatment to the date of death from any cause or last contact (censored observations).

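### The stage-1 futility look may fall 8 weeks after subject 15 enrols, before that patient could have a confirmed iRANO response, so the look can stop an active arm more often than the design allows

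*Combined protocol and SAP*

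**What the plan says.** Section 13.5 places the stage-1 look after 15 patients per arm. Once subject 15 is enrolled, "we will wait a minimum of 8 (median time to response) and maximum of 12 weeks". As written, this wait applies when no iRANO response has yet been noted in the arm. The section says that early stopping will be considered, and gives 65% as the chance of stopping under the null. It does not say whether an unconfirmed response counts at the look.

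The primary endpoint has its own clock. Section 13.2 counts a best response after at least 6 weeks of therapy and adds: "iRANO additionally requires best overall response of CR or PR to be sustained, that is, confirmed by a second assessment at" four weeks or more. Section 11.1 schedules scans about every 6 weeks from first dose. Section 1.1 allows up to a week between enrolment and first infusion.

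The design is in section 13.1: "the null H0 is set at 14% and H1 (target ORR) set at 35% for each arm", and "Power is set at 85% with a 1-sided alpha of 0.05". It gives two stage-1 rules. One closes the arm at zero: "If no response is seen after 15 eligible patients are accrued in either arm, that arm will close for futility". The other, attributed to Minimax, sets the bar for going on: "if >2 responses are seen on the first 15 patients in either arm, then 15 more patients will be accrued in the arm". At the end, the bar is met if at least "7 responses are seen among the 30 patients in either arm, this regimen deserves further investigation".

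**The concern.** A two-stage design has its stated error rates only if stage-1 responses are complete when counted. Here the wait can be shorter than the time needed to establish a response. A patient who is going to respond, but has not yet been scanned or confirmed, is counted as a failure. Section 13.5 describes the 8 weeks as the median time to response. On the plan's own figure, then, about half of eventual responses in the newest patients would come later.

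Under the >2/15 rule the error runs one way: missing responses can only add futility stops. An active arm could be closed because of when it was looked at, and that is not reversible.

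**Working it through.** **1. Reproduce the plan's figures.** Let X1 and X2 be responses in the two stages, each Bin(15, p). Stop if X1 ≤ 2; succeed if X1 + X2 ≥ 8.

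- Stopping at p = 0.14: 0.1041 + 0.2542 + 0.2897 = 0.648. The plan says 65%.
- Stopping at p = 0.35: 0.0016 + 0.0126 + 0.0476 = 0.062.
- Power at 0.35: Σ over x = 3 to 15 of P(X1 = x)·P(X2 ≥ 8 − x) = 0.852. The plan says 85%.
- Alpha at 0.14, same sum: 0.0455.

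So >2/15 with 8/30 is the design behind the stated 85%, 0.05 and 65%. The other written rules do not give these figures. With ≥7/30 and >2/15, alpha is 0.099 and power 90.5%. Closing only at 0/15 stops under the null 0.86^15 = 10.4% of the time.

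**2. Earliest confirmed response.** Week 6 + 4 weeks = week 10 from first dose. A response first seen at week 12 is confirmed at week 16 at the earliest. Twelve weeks from enrolment is at least 11 weeks from first dose, so a week-6 response can be confirmed by then.

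**3. Effect of the 10-week floor alone.** Section 13.3 expects two patients per month. I assume an even split, one per arm per month (4.33 weeks apart). At an 8-week look subject 14 has 8 + 4.33 = 12.3 weeks of follow-up, so only subject 15 is lost. Stopping at 35% becomes P(Bin(14, 0.35) ≤ 2) = 0.0024 + 0.0181 + 0.0634 = 0.084, and power is 0.838, a loss of 1.4 points. At 12 weeks nothing is lost.

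**4. Responses that appear after week 6 (assumption).** The documents give no distribution of response times. For subject i and a wait of w weeks, the last scan that can already be confirmed is number k = floor((w + 4.33(15 − i) − 4)/6). The chance that an eventual response is countable is F(6k), and the final analysis counts every response. With F lognormal, sigma 0.5, median 2 months (8.67 weeks), and w = 12:

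- Subject 15: k = 1, F(6) = Φ(ln(6/8.67)/0.5) = 0.23.
- Subject 14: k = 2, F(12) = 0.74.

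Results for a 35% arm under >2/15 and 8/30, confirmed responses only:

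| Response timing | 8-week look: stop / power | 12-week look: stop / power |
|---|---|---|
| Complete follow-up (design) | 6.2% / 85.2% | 6.2% / 85.2% |
| All visible at week 6 | 8.4% / 83.8% | 6.2% / 85.2% |
| Half at week 6, half at week 12 | 9.9% / 82.7% | 7.3% / 84.5% |
| Lognormal, median 2 months, regular accrual | 13.0% / 80.4% | 9.8% / 82.8% |
| Same, random arrivals | 16.4% / 77.6% | 11.9% / 81.1% |
| Exponential, median 2 months, regular accrual | 16.4% / 77.6% | 12.6% / 80.6% |
| Lognormal, median 3 months, regular accrual | 18.4% / 76.1% | 14.2% / 79.4% |
| Same, random arrivals | 22.9% / 72.1% | 17.5% / 76.7% |

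**5. Effect of counting unconfirmed CR/PR at 12 weeks.** Drop the 4 from k. With random arrivals, stopping is 8.1% and power 83.9% (median 2 months), or 12.1% and 80.9% (median 3 months).

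**The case against.** **The written rules differ from the ones modelled.** Section 13.1's only explicit closure rule is zero responses in 15, and the condition in section 13.5 that no response has yet been noted fits that rule. If it governs, wrongful stopping at the assumed accrual is at most 1.3% and power stays at about 87% or more, even with late responders. This stands as a reading of the text. But it implies 10.4% stopping under the null, not the 65% in section 13.5, so the plan's own operating characteristics belong to >2/15. The written ≥7/30 also cushions power: with >2/15, random arrivals and a 2-month median it is about 81% at 8 weeks and 85.5% at 12. The price is an alpha of 0.099.

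**The loss provable from the documents is small.** This stands: 1.4 points at 8 weeks, none at 12. Everything beyond that depends on an assumed spread of response times.

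**Confirmed-only counting is not stated for the look.** Also true. The silence is part of the problem, because section 13.2 makes confirmation part of an iRANO response.

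Two stronger readings are tempting. A reader might take the background figure in section 2.4.3, "There was a longer time to best response (3.0 vs. 1.5 months", as showing that the median should be 3 months rather than 2. It is time to best response on nivolumab alone, and best response can come after first response, so the 3-month rows are only a sensitivity case. A reader might also take the 8-week persistence in the CR and PR criteria of section 11.3 to put the earliest response at week 14, beyond even the 12-week limit. The same items also refer to a confirming scan at 4 weeks, and section 13.2 uses 4 weeks for iRANO, so the documents do not settle on 8.

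**Conclusion.** The timing conflict is real and lies in the plan's own text: the 8-week minimum is shorter than the 10 weeks that a confirmed response needs. Under >2/15 and 8/30 this raises wrongful stopping of a 35% arm above the designed 6.2%. The certain part, at an 8-week look, is 8.4% stopping and 83.8% power. With a 2-month lognormal median, one patient per arm per month and confirmed responses only, the two looks span roughly 10% to 16% stopping and 78% to 83% power. A 3-month median gives about 72% to 79% power.

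A reader might infer that the stated 85% power is simply not delivered. The documents do not support that as a fact. It depends on which stage-1 rule and final cut-off govern, on when in the 8-to-12-week window the look falls, on whether unconfirmed responses count, and on response timing that the plan does not specify. What can be said is that the plan leaves room for a loss that clearer wording would reduce.

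**What to change.** In section 13.5:

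1. State that any CR or PR seen by the look, confirmed or not, counts towards continuing. Keep the final count confirmed-only.
2. Hold the look no earlier than 12 weeks after subject 15 starts treatment, whether or not a response has already been noted. At present no wait is specified for an arm with one or two responses, which is still short of >2.

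This is a wording change. It adds at most about a week to the present 12-week maximum, because first infusion can follow enrolment by up to a week. In the 2-month random-arrival case power rises to 83.9%, from 77.6% at 8 weeks (6.3 points) or 81.1% at 12 weeks (2.8 points).

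The cost is a slightly higher chance of continuing an inactive arm. In the same model at p = 0.14, null stopping at 12 weeks moves from 72.7% to 67.7%, still above the designed 64.8%. Responses that later fail to confirm are not modelled and would lower it further. Type I error is not at risk with 8/30: even with no stopping, P(Bin(30, 0.14) ≥ 8) = 0.0497.

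Waiting about 22 weeks (week-18 scan plus 4) with confirmed-only counting gives 6.7% stopping and 84.9% power at a 2-month median, or 8.5% and 83.6% at 3 months. It is optional, because it could hold accrual about 10 weeks longer.

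The two stage-1 rules and the 7-versus-8 final cut-off in section 13.1 must be reconciled separately.

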APPENDIX A Karnofsky Performance Status (KPS) Criteria

Percent	Description
100	Normal, no complaints, no evidence of disease.
90	Able to carry on normal activity; minor signs or symptoms of disease.
80	Normal activity with effort; some signs or symptoms of disease.
70	Cares for self, unable to carry on normal activity or to do active work.
60	Requires occasional assistance, but is able to care for most of his/her needs.
50	Requires considerable assistance and frequent medical care.
40	Disabled, requires special care and assistance.
30	Severely disabled, hospitalization indicated. Death not imminent.
20	Very sick, hospitalization indicated. Death not imminent.
10	Moribund, fatal processes progressing rapidly.
0	Dead.

APPENDIX B

Neurologic Assessment In Neuro-Oncology (NANO) Scale

Scoring assessment is based on direct observation and testing performed during clinical evaluation and is not based on historical information or reported symptoms. Please check 1 answer per domain. Please check "Not assessed" if testing for that domain is not done. Please check "Not evaluable" if a given domain cannot be scored accurately due to pre-existing conditions, co-morbid events and/or concurrent medications.

Study #, Participant # and Initials:	/
Domains Gait 0 Normal 1 Abnormal but walks without assistance 2 Abnormal and requires assistance (companion, cane, walker, etc.) 3 Junable to walk Unable to walk	 Key Considerations Walking is ideally assessed by at least 10 steps
 Not assessed Not evaluable 	
Strength 0 Normal 1 Movement present but decreased against resistance 2 Movement present but none against resistance 3 No movement Not assessed Not evaluable	 Test each limb separately Recommend assess proximal (above knee or elbow) and distal (below knee or elbow) major muscle groups Score should reflect worst performing area Patients with baseline level 3 function in one major muscle group/limb can be scored based on assessment of other major muscle groups/limb
Ataxia (upper extremity) 0 Able to finger to nose touch without difficulty 1 Able to finger to nose touch but difficult 2 Unable to finger to nose touch Not assessed Not evaluable	 Non-evaluable if strength is compromised Trunk/lower extremities assessed by gait domain Particularly important for patients with brainstem and cerebellar tumors Score based on best response of at least 3 attempts
Sensation 0 Normal 1 Decreased but aware of sensory modality 2 Unaware of sensory modality Not assessed Not evaluable Study #, Participant # and Initials: Date Assessment Performed (day/month/year);	 Recommend evaluating major body areas separately (face, limbs and trunk) Score should reflect worst performing area Sensory modality includes but not limited to light touch, pinprick, temperature and proprioception Patients with baseline level 2 function in one major body area can be scored based on assessment of other major body areas
Study time point (i.e. cycle 1, day 1, etc.):	

0 Normal

- 2 ☐ Consistent or unequivocal partial hemianopsia (≥quadrantopsia)
- 3 Complete hemianopsia
 - Not assessed
 - Not evaluable

Facial Strength

- 0 Normal
- 1 Mild/moderate weakness
- 2 Severe facial weakness
 - Not assessed
 - Not evaluable

Language

- 0 Normal
- 1 Abnormal but easily conveys meaning to examiner
- 2 Abnormal and difficulty conveying meaning to examiner
- 3 Abnormal. If verbal, unable to convey meaning to examiner. OR non-verbal (mute/global aphasia)
 - Not assessed
 - Not evaluable

Level of Consciousness

- 0 Normal
- 1 Drowsy (easily arousable)
- $2 \square$ Somnolent (difficult to arouse)
- 3 Unarousable/coma
 - Not assessed
 - Not evaluable

Behavior

- 0 🗌 Normal
- 1 Mild/moderate alteration
- 2 Severe alteration
 - Not assessed
 - Not evaluable

- Patients who require corrective lenses should be evaluated while wearing corrective lenses
- Each eye should be evaluated and score should reflect the worst performing eye
- Particularly important for brainstem tumors
- Weakness includes nasolabial fold flattening, asymmetric smile and difficulty elevating
- Assess based on spoken speech. Non-verbal cues or writing should not be included.
- Level 1: Includes word finding difficulty; few paraphrasic errors/neologisms/word substitutions; but able to form sentences (full/broken)
- Level 2: Includes inability to form sentences (<4 words per phrase/sentence); limited word output; fluent but "empty" speech.
- None

- Particularly important for frontal lobe tumors
- Alteration includes but is not limited to apathy, disinhibition and confusion
- Consider subclinical seizures for significant alteration

APPENDIX C Functional Assessment of Cancer Therapy-Brain 4.0 (FACT-Br)

FACT-Br (Version 4)

Below is a list of statements that other people with your illness have said are important. Please circle or mark one number per line to indicate your response as it applies to the past 7 days.

	PHYSICAL WELL-BEING	Not at all	A little bit	Some- what	Quite a bit	Very much
GP1	I have a lack of energy	0	1	2	3	4
GP2	I have nausea	0	1	2	3	4
GP3	Because of my physical condition, I have trouble meeting the needs of my family	0	1	2	3	4
GP4	I have pain	0	1	2	3	4
GP5	I am bothered by side effects of treatment	0	1	2	3	4
GP6	I feel ill	0	1	2	3	4
GP7	I am forced to spend time in bed	0	1	2	3	4
	SOCIAL/FAMILY WELL-BEING	Not at all	A little bit	Some- what	Quite a bit	Very much
G S1	I feel close to my friends	0	1	2	3	4
G S2	I get emotional support from my family	0	1	2	3	4
G S3	I get support from my friends	0	1	2	3	4
G S4	My family has accepted my illness	0	1	2	3	4
G S5	I am satisfied with family communication about my illness	0	1	2	3	4
G \$6	I feel close to my partner (or the person who is my main support)	0	1	2	3	4
Q1	Regardless of your current level of sexual activity, please answer the following question. If you prefer not to answer it, please mark this box and go to the next section.					
GS7	I am satisfied with my sex life	. 0	1	2	3	4

English (Universal) Copyright 1987, 1997 16 November 2007 Page 1 of 3

FACT-Br (Version 4)

Please circle or mark one number per line to indicate your response as it applies to the past 7 days.

	EMOTIONAL WELL-BEING	Not at all	A little bit	Some- what	Quite a bit	Very much
GE1	I feel sad	0	1	2	3	4
GE2	I am satisfied with how I am coping with my illness	0	1	2	3	4
GE3	I am losing hope in the fight against my illness	0	1	2	3	4
GE4	I feel nervous	0	1	2	3	4
GE5	I worry about dying	0	1	2	3	4
GE6	I worry that my condition will get worse	0	1	2	3	4

	FUNCTIONAL WELL-BEING	Not at all	A little bit	Some- what	Quite a bit	Very much
GF1	I am able to work (include work at home)	. 0	1	2	3	4
GF2	My work (include work at home) is fulfilling	. 0	1	2	3	4
GF3	I am able to enjoy life	. 0	1	2	3	4
GF4	I have accepted my illness	. 0	1	2	3	4
GF5	I am sleeping well	. 0	1	2	3	4
GF6	I am enjoying the things I usually do for fun	. 0	1	2	3	4
GF7	I am content with the quality of my life right now	. 0	1	2	3	4

English (Universal) Copyright 1987, 1997 16 November 2007 Page 2 of 3

FACT-Br (Version 4)

Please circle or mark one number per line to indicate your response as it applies to the past 7 days.

	ADDITIONAL CONCERNS	Not at all	A little bit	Some- what	Quite a bit	Very much
Br1	I am able to concentrate	. 0	1	2	3	4
Br2	I have had seizures (convulsions)	. 0	1	2	3	4
Br3	I can remember new things	. 0	1	2	3	4
Br4	I get frustrated that I cannot do things I used to	. 0	1	2	3	4
Brð	I am afraid of having a seizure (convulsion)	. 0	1	2	3	4
Bró	I have trouble with my eyesight	. 0	1	2	3	4
Br7	I feel independent	. 0	1	2	3	4
NTX6	I have trouble hearing	. 0	1	2	3	4
Br8	I am able to find the right word(s) to say what I mean	. 0	1	2	3	4
Br9	I have difficulty expressing my thoughts	0	1	2	3	4
Br10	I am bothered by the change in my personality	. 0	1	2	3	4
Br11	I am able to make decisions and take responsibility	0	1	2	3	4
Br12	I am bothered by the drop in my contribution to the family	0	1	2	3	4
Br13	I am able to put my thoughts together	. 0	1	2	3	4
Br14	I need help in caring for myself (bathing, dressing, eating, etc.)	0	1	2	3	4
Br15	I am able to put my thoughts into action	. 0	1	2	3	4
Br16	I am able to read like I used to	. 0	1	2	3	4
Br17	I am able to write like I used to	. 0	1	2	3	4
Br18	I am able to drive a vehicle (my car, truck, etc.)	. 0	1	2	3	4
Br19	I have trouble feeling sensations in my arms, hands, or legs	. 0	1	2	3	4
Br20	I have weakness in my arms or legs	. 0	1	2	3	4
Br21	I have trouble with coordination	. 0	1	2	3	4
An10	I get headaches	0	1	2	3	4

English (Universal) Copyright 1987, 1997 16 November 2007 Page 3 of 3

Refer to: www.facit.org

APPENDIX D

TTFields Compliance Reports Generated by NovoTTF200A (OptuneTM)

Panels show example graphs of compliance: Top = Low compliance; Middle = Compliance near goal; Bottom = Compliance above goal of 75%. The report also includes the number of days included, which allows calculation of weighted averages across the duration of TTFields therapy.

APPENDIX E Toxicity Management Algorithms for Nivolumab (Appendix 3 of Investigator Brochure BMS-936558/MDX1106/ONO-4538)

Investigator Brochure BMS-936558/MDX1106/ONO-4538

nivolumab

Appendix 3: Management Algorithms

These general guidelines constitute guidance to the Investigator and may be supplemented by discussions with the Medical Monitor representing the Sponsor. The guidance applies to all immuno-oncology agents and regimens.

A general principle is that differential diagnoses should be diligently evaluated according to standard medical practice. Non-inflammatory etiologies should be considered and appropriately treated.

Corticosteroids are a primary therapy for immuno-oncology drug-related adverse events. The oral equivalent of the recommended IV doses may be considered for ambulatory patients with low-grade toxicity. The lower bioavailability of oral corticosteroids should be taken into account when switching to the equivalent dose of oral corticosteroids.

Consultation with a medical or surgical specialist, especially prior to an invasive diagnostic or therapeutic procedure, is recommended.

The frequency and severity of the related adverse events covered by these algorithms will depend on the immuno-oncology agent or regimen being used.

Approved V17.0 930038243 18.0

245

Investigator Brochure BMS-936558/MDX1106/ONO-4538

nivolumab

GI Adverse Event Management Algorithm

Rule out non-inflammatory causes. If non-inflammatory cause is identified, treat accordingly and continue I-O therapy. Opiates/narcotics may mask symptoms of perforation. Infliximab should not be used in cases of perforation or sepsis.

Patients on IV steroids may be switched to an equivalent dose of oral corticosteroids (e.g. prednisone) at start of tapering or earlier, once sustained clinical improvement is observed. Lower bioavailability of oral corticosteroids should be taken into account when switching to the equivalent dose of oral corticosteroids. Investigator Brochure

BMS-936558/MDX1106/ONO-4538

nivolumab

Renal Adverse Event Management Algorithm

Rule out non-inflammatory causes. If non-inflammatory cause, treat accordingly and continue I-O therapy

Patients on IV steroids may be switched to an equivalent dose of oral corticosteroids (e.g. prednisone) at start of tapering or earlier, once sustained clinical improvement is observed. Lower bioavailability of oral corticosteroids should be taken into account when switching to the equivalent dose of oral corticosteroids. Investigator Brochure BMS-936558/MDX1106/ONO-4538

nivolumab

Pulmonary Adverse Event Management Algorithm

Rule out non-inflammatory causes. If non-inflammatory cause, treat accordingly and continue I-O therapy. Evaluate with imaging

Investigator Brochure BMS-936558/MDX1106/ONO-4538

nivolumab

Hepatic Adverse Event Management Algorithm

Rule out non-inflammatory causes. If non-inflammatory cause, treat accordingly and continue I-O therapy. Consider imaging for obstruction

Patients on IV steroids may be switched to an equivalent dose of oral corticosteroids (e.g. prednisone) at start of tapering or earlier, once sustained clinical improvement is observed. Lower bioavailability of oral corticosteroids should be taken into account when switching to the equivalent dose of oral corticosteroids. *I-O therapy may be delayed rather than discontinued if AST/ALT < 8 x ULN or T.bili < 5 x ULN.

**The recommended starting dose for grade 4 hepatitis is 2 mg/kg/day methylprednisolone IV.

Investigator Brochure BMS-936558/MDX1106/ONO-4538

nivolumab

Endocrinopathy Management Algorithm Rule out non-inflammatory causes. If non-inflammatory cause, treat accordingly and continue I-O therapy. Consider visual field testing, endocrinology consultation, and imaging. Continue I-O therapy per protocol Asymptomatic • If TSH < 0.5 x LLN, or TSH > 2 x ULN, or consistently out of range in 2 subsequent measurements: include fT4 at **TSH elevation** subsequent cycles as clinically indicated; consider endocrinology consult If improves (with or without Evaluate endocrine function hormone replacement): Consider pituitary scan Taper steroids over at least 1 month and consider prophylactic Symptomatic with abnormal lab/pituitary scan: antibiotics for opportunistic Symptomatic Delay I-O therapy per protocol infections endocrinopathy Resume I-O therapy per protocol 1-2 mg/kg/day methylprednisolone IV or PO equivalent Initiate appropriate hormone therapy Patients with adrenal insufficiency may need to No abnormal lab/pituitary MRI scan but symptoms persist: continue steroids with • Repeat labs in 1-3 weeks / MRI in 1 month mineralocorticoid component Suspicion of adrenal Delay or discontinue I-O therapy per protocol crisis (e.g. severe Rule out sepsis Stress dose of IV steroids with mineralocorticoid activity dehydration, • IV fluids hypotension, shock **Consult endocrinologist** out of proportion to · If adrenal crisis ruled out, then treat as above for symptomatic current illness endocrinopathy Patients on IV steroids may be switched to an equivalent dose of oral corticosteroids (e.g. prednisone) at start of tapering or earlier, once sustained clinical improvement is observed. Lower bioavailability of oral corticosteroids should be taken into account when switching to the equivalent dose of oral corticosteroids.

Investigator Brochure BMS-936558/MDX1106/ONO-4538

nivolumab

Skin Adverse Event Management Algorithm

Rule out non-inflammatory causes. If non-inflammatory cause, treat accordingly and continue I-O therapy.

Patients on IV steroids may be switched to an equivalent dose of oral corticosteroids (e.g. prednisone) at start of tapering or earlier, once sustained clinical improvement is observed. Lower bioavailability of oral corticosteroids should be taken into account when switching to the equivalent dose of oral corticosteroids. *Refer to NCI CTGLE 44 for term-specific grading criteria.

Alf SJS/TEN is suspected, withhold I-O therapy and refer patient for specialized care for assessment and treatment. If SJS or TEN is diagnosed, permanently discontinue I-O therapy.

nivolumab

Neurological Adverse Event Management Algorithm

Rule out non-inflammatory causes. If non-inflammatory cause, treat accordingly and continue I-O therapy.

Patients on IV steroids may be switched to an equivalent dose of oral corticosteroids (e.g. prednisone) at start of tapering or earlier, once sustained clinical improvement is observed. Lower bioavailability of oral corticosteroids should be taken into account when switching to the equivalent dose of oral corticosteroids.

APPENDIX F Toxicity Management Algorithms for Ipilimumab (Appendix 3 of Investigator Brochure BMS-734016/MDX-010)

equivalent dose of PO corticosteroids.

Investigator Brochure BMS-734016/MDX-010

Ipilimumab

Investigator Brochure BMS-734016/MDX-010

Ipilimumab

Skin Toxicity Management Algorithm

Patients on IV steroids may be switched to oral corticosteroid (e.g., prednisone) at an equivalent dose at start of tapering or earlier, once sustained clinical improvement is observed. Lower bioavailability of oral corticosteroids should be taken into account when switching to the equivalent dose of PO corticosteroids. Investigator Brochure BMS-734016/MDX-010

Ipilimumab

Endocrinopathy Management Algorithm

Investigator Brochure BMS-734016/MDX-010

Ipilimumab

Neurological Toxicity Management Algorithm

Patients on IV steroids may be switched to oral corticosteroid (e.g., prednisone) at an equivalent dose at start of tapering or earlier, once sustained clinical improvement is observed. Lower bioavailability of oral corticosteroids should be taken into account when switching to the equivalent dose of PO corticosteroids.
